3.1.3 Exploratory Endpoints

- Median duration of overall survival
- Pharmacokinetics

3.2 Safety

3.2.1 Definitions

3.2.1.1 *Adverse Events*

An AE is any unfavorable and unintended sign (including an abnormal laboratory finding), symptom, or disease temporally associated with the use of a medical treatment or procedure that may or may not be considered related to the medical treatment or procedure. Assessment of the occurrence of an AE will be based on changes in the patient's physical examination, laboratory results, and/or signs and symptoms. An AE also includes any newly occurring event or previous condition that has increased in severity or frequency from signing the informed consent.

Adverse events will be monitored until they are resolved or clearly determined to be due to a patient's stable or chronic condition or intercurrent illness(es). Medical care will be provided, as defined in the informed consent, for any AE related to study participation.

3.2.1.2 *Serious Adverse Event*

A serious adverse event (SAE) is any untoward medical occurrence resulting in the following:

- Death
- Is life-threatening (defined as an event in which the patient was at risk of death at the time of the event; it does not refer to an event which hypothetically might have caused death if it were more severe)
- Requires in-patient hospitalization or causes prolongation of existing hospitalization
- Results in persistent or significant disability/incapacity
- Is a congenital anomaly/birth defect
- Is an important medical event (defined as a medical event(s) that may not be immediately life-threatening or result in death or hospitalization, but, based upon appropriate medical and scientific judgment, may jeopardize the patient or may require intervention [e.g., medical or surgical] to prevent one of the other serious outcomes listed in the definition above). Examples of such events include, but are not limited to, intensive treatment in an emergency room or at home for allergic bronchospasm; blood dyscrasias or convulsions that do not result in hospitalization.

Although overdose is not always serious by regulatory definition, this event should be reported on an SAE form and sent to the sponsor in an expedited manner.

All pregnancies, regardless of outcome, must be reported to the sponsor on a pregnancy form, not an SAE form.

NOTE:

The following hospitalizations are not considered SAEs in sponsor clinical studies:

- A visit to the emergency room or other hospital department lasting <24 hours, that does not result in admission (unless considered “important medical event” or event that is “life-threatening”)
- Elective surgery planned prior to signing consent
- Admissions as per protocol for a planned medical/surgical procedure
- Routine health assessment requiring admission for pretreatment assessment/trending of health status (e.g., routine colonoscopy)
- Medical/surgical admission for purpose other than remedying ill health state and was planned prior to signing consent. Appropriate documentation is required in these cases
- Admission encountered for another life circumstance that carries no bearing on health status and requires no medical/surgical intervention (e.g., lack of housing, economic inadequacy, care-giver respite, family circumstances, administrative)
- Admission for Progressive Disease (PD)

3.2.2 Period of Observation

All AEs (including SAEs) regardless of the relationship to study drug or study procedure will be collected from obtaining informed consent to the EoT assessment. At EoT, AEs Grade ≥ 2 considered to be at least possibly related to the study drug must be followed up after the EoT assessment until the events have recovered to Grade ≤ 1 , returned to the baseline level, are judged by the investigator to be stabilized, or to be given a reason that further follow up will not be required (see Section 2.6.4). However, if the patient begins to receive new cancer therapy or withdraws consent to study participation, no further follow-up will be conducted. The outcome of the events which do not resolved by that time will be recorded as “ongoing” on the eCRF.

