2.6.4 End of Treatment Safety Follow-up Visit

All patients receiving at least one dose of HBI-8000 and discontinuing treatment for any reason except death will be assessed 30 (\pm 3) days after the last dosing of study drug, before the initiation of new cancer treatment or before the initiation of administration of commercial product of HBI-8000, whichever is earlier. Any patient for whom study treatment has been discontinued should complete study procedures listed in the EoT visit. At EoT safety visit, evaluations will include physical examination, vital signs, body weight, ECOG performance

status, hematology, blood chemistry, urinalysis, pregnancy test (if applicable), ECG, and assessment of any ongoing adverse events. If a patient discontinues study treatment before PD is recorded, and if the last tumor assessment was >30 days earlier from the EoT visit, tumor assessment should be performed at EoT. In these patients, further tumor assessments are to be performed approximately every 3 months \pm 2 weeks until PD or the start of new cancer therapy whichever occurs first, unless consent to study participation is withdrawn or by completion of the whole study. If subjects cannot visit at site for this examination due to COVID-19 situation, investigators can skip the examination, and the assessment is to be performed approximately every 6 months \pm 2 weeks. In this case, the investigator should document that fact in the medical record.

Patients with HBI-8000-related AEs of Grade ≥ 2 observed at the EoT visit should be followed-up and assessed monthly (phone calls/clinic visits) until the AEs have resolved to Grade ≤ 1 or are determined to be chronic, or patient receives other anti-cancer therapy.

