5.10.1 Adverse Events

Adverse events will be classified using the MedDRA classification system version 19.0 or higher. The severity of the toxicities will be graded according to the NCI CTCAE version 4.03.

In all summaries, emphasis will be placed on treatment emergent adverse events (TEAEs), namely, those with initial onset or that worsen in severity after the first dose of HBI-8000. TEAEs will be summarized by the frequency of patients experiencing TEAEs corresponding to body systems and MedDRA preferred term and by worst NCI CTCAE (version 4.03) grade. Summaries will also be provided of treatment related TEAEs, namely, those judged by the investigator to be related or likely related to HBI-8000.

TEAEs resulting in discontinuation of HBI-8000 treatment or withdrawal from the study, Grade 3 or higher, SAEs, and deaths on-study will be tabulated.

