9.0 APPENDICES

9.1 Appendix A: HBI-8000-203 Schedule of Events

Table 4: Schedule of Events

	Screening	Cycle 1				Cycle 2			Cycle $\geq 3^a$	EoT ^b	Survival F/U ^c
DAY	-28 to 0	1	8±2	15±2	22±2	1±4	15±4	1±7			
		Pre-dose ^d	3.5 hrs			Pre-dose	3.5 hrs		Pre-dose		
HBI-8000 ^d		BIW ^e				BIW ^e			BIW ^e		
Written informed consent	X										
Medical history, diagnosis and treatment history, demographics, height	X										
Physical examination, weight	X	X			X	X		X	X	X	
ECOG Performance Status	X	X				X			X	X	
Vital signs ^f	X	X			X	X		X	X	X	
12 Lead ECG (Safety)	X								X	X	
12 Lead ECG (QTc)		X ^g	X ^g			X ^g	X ^g				
Hematology ^h	X	X		X	X	X		X	X	X	
Coagulation ^h	X	X		X		X			X		
Chemistry ⁱ	X	X		X	X	X		X	X	X	
Urinalysis ^j	X	X								X	
Hepatitis B/C virus tests ^k	X										
Serum pregnancy test (if applicable) ^l	X	X								X	
Tumor assessment ^m	X								X ^m	X ^m	X ^m
PK blood samples		X ⁿ				X ⁿ			X ^o		
Patient survival; new cancer therapies											X

	Screening	Cycle 1				Cycle 2		Cycle $\geq 3^a$	EoT ^b	Survival F/U ^c
DAY	-28 to 0	1	8±2	15±2	22±2	1±4	15±4	1±7		
		Pre-dose ^d	3.5 hrs			Pre-dose	3.5 hrs		Pre-dose	
Adverse events assessment	X	X	X	X	X	X	X	X	X	
Concomitant medication	X	X	X	X	X	X	X	X	X	

Abbreviations: ALT, alanine aminotransferase; aPTT, activated partial thromboplastin time; AST, aspartate aminotransferase; BIW, twice weekly; BUN, blood urea nitrogen; ECG, electrocardiogram; ECOG, Eastern Cooperative Oncology Group; EoT, end of treatment; F/U, follow-up; GGT, gamma-glutamyl transpeptidase; INR, international normalized ratio; LDH, lactate dehydrogenase; mSWAT, Modified Severity-Weighted Assessment Tool; PET-CT, positron emission tomography-computer tomography; PCR, polymerase chain reaction; PK, pharmacokinetic; PT, prothrombin time;

- a Cycle/Day designation is based on actual calendar days after the first dose. All visits and assessments may be performed ± 7 days to accommodate unforeseen delays, holidays, or vacations.
- b “End of Treatment” visit should be conducted 30 ± 3 days after the last dosing of the study drug, before the initiation of new cancer treatment or before the initiation of administration of commercial product of HBI-8000, whichever is earlier.
- c Survival data will be collected every 3 months ± 2 weeks after End of Treatment until death or the end of the study, defined as timing that the last Japanese subject initiates administration of the commercial product of HBI-8000.

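### Adverse event collection stops at an end-of-treatment visit with no minimum time after the last dose, so a drug-related SAE that begins after an early visit has no stated collection route

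*Combined protocol and SAP*

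**What the plan says.** Section 3.2.2 fixes both ends of the collection period: "All AEs (including SAEs) regardless of the relationship to study drug or study procedure will be collected from obtaining informed consent to the EoT assessment". It makes no exception for drug-related events.

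The date of EoT varies. Footnote b to Table 4 says that the "visit should be conducted 30 ± 3 days after the last dosing of the study drug", and section 2.6.4 adds the triggers that bring it forward: "before the initiation of new cancer treatment or before the initiation of administration of commercial product of HBI-8000, whichever is earlier". Section 2.6.6 repeats the rule. The visit applies to treated patients "discontinuing treatment for any reason except death will be assessed".

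After EoT, two things continue:

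- **Related Grade ≥2 AEs present at EoT.** Section 3.2.2 says that those "considered to be at least possibly related to the study drug must be followed up after the EoT assessment until the events have recovered" or meet another stopping condition. It then limits this: "However, if the patient begins to receive new cancer therapy or withdraws consent to study participation, no further follow-up will be conducted". Section 2.6.4 has the same limit.
- **Survival status.** Section 2.6.5 and Table 4 footnote c collect it about every 3 months until death or end of study. Section 2.6.5 also records the regimen and start date of the first subsequent anticancer therapy.

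For the analysis, section 5.10.1 defines treatment-emergent events by a start (after the first dose) but gives no end. It says that, among other categories, "SAEs, and deaths on-study will be tabulated", without saying what on-study means.

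**The concern.** The period in which a new adverse event can enter the database is set by the patient's next treatment, not by time since the last dose. Two patients with the same last dose and the same later event can be counted differently only because one of them started another therapy.

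Safety and tolerability are the secondary objective (section 2.2), and section 5.1 calls the study pivotal for approval. What could be lost is a specific class of event: serious, attributable to HBI-8000, and beginning after an EoT visit that was brought forward. The safeguard for related Grade ≥2 events does not help, because it covers only events already present at EoT and ends when new cancer therapy starts. With no definition of on-study deaths, that table could also cover a different post-dose period in each patient.

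**Working it through.** No sample-size or error-rate figure bears on this. The check takes the rule from the text and then follows individual events through it.

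**1. Length of the window.** Let *d* be the day, counted from the last dose, on which new cancer therapy or commercial HBI-8000 starts. The visit must come before that start, so

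window ≤ min(27 to 33 days, *d*).

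Without a trigger, this returns the plan's own figure: 30 − 3 = 27 to 30 + 3 = 33 days. With a trigger, no lower limit is stated. The documents give no values for *d*, so those below are assumptions that show the range.

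| Assumed *d* | Window at most | Share of 30 days | Days lost |
|---|---|---|---|
| 1 | 1 day | 1/30 = 3% | 29 |
| 3 | 3 days | 3/30 = 10% | 27 |
| 7 | 7 days | 7/30 = 23% | 23 |
| 14 | 14 days | 14/30 = 47% | 16 |
| 21 | 21 days | 21/30 = 70% | 9 |
| no new therapy | 27 to 33 days | nominal | 0 |

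**2. Three events traced through the rules.** Patient A starts new cancer therapy on day 7 (assumed), so EoT falls by day 7. Patient B starts nothing, so EoT falls on days 27 to 33.

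| Event | Patient A | Patient B |
|---|---|---|
| Drug-related SAE with onset on day 12 | After EoT; no section provides for collection | Before EoT; collected |
| Related Grade 2 AE still present on day 7 | Follow-up ends when the new therapy starts; left as ongoing | Collection and follow-up continue |
| Death on day 20 | Recorded in survival follow-up; no SAE form or causality opinion called for | Before EoT; collected as an SAE with causality |

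**3. Is there another route?** Section 3.2.7.1 gives reporting timelines for SAEs and for suspected unexpected serious reactions. It states no end date, but it does not reopen the collection period that 3.2.2 closes. Section 3.2.7.2 runs pregnancy reporting to 1 month after the last dose for patients and 3 months for partners of male patients. Neither is tied to EoT, so the protocol already uses fixed post-dose windows for another safety item.

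**4. Can deaths within 30 days be counted?** Yes. The calculation is date of death minus date of last dose ≤ 30, and both come from data already planned. Patient A's death (20 ≤ 30) counts. The exceptions are patients who withdraw from the study entirely (no further follow-up under 2.6.6) and any whose survival follow-up ends with the study before day 30.

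**5. Study-level loss.** This needs the share of patients who switch before day 30 and the day on which they switch. The documents give neither, so no total is offered.

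**The case against.** The rule is consistent wherever it appears, and it looks deliberate. In a single-arm study, stopping routine AE collection before the next anticancer drug keeps that drug's toxicity out of the HBI-8000 profile. This stands, and it is why the routine cut-off should stay.

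Inclusion criterion 3 requires that no other standard treatment is considered appropriate, which makes a very early switch less plausible as a common pattern. This also stands, and it limits how often the gap would open. It does not close the gap, because 2.6.4 to 2.6.6 plainly expect new cancer treatment to follow.

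It can be said that 3.2.7.1 sets no end to SAE reporting. An investigator might report a late event on that basis, but 3.2.2 is the section that defines what is collected, and it stops at EoT.

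The change also comes late. Last patient in was planned for 3Q 2018 and this version is dated July 2021, so new reporting wording reaches only patients not yet past EoT. The commercial-product trigger operates after approval, so it should not touch the main analysis prepared for submission. Both points stand. Neither affects the 30-day death table, which uses data already planned.

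**Conclusion.** The gap is real but narrow. Followed as written, the plan has no stated route for a drug-related SAE that begins after an early EoT. The post-dose window varies between patients, up to 33 days, with no minimum. On-study deaths are undefined. This affects the completeness and comparability of safety reporting; it has no bearing on the ORR analysis or the sample size.

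Several stronger readings are tempting, and the documents do not support them:

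- **That deaths go uncollected after EoT.** Survival follow-up continues to death or end of study. What is lost is the SAE report and causality opinion for deaths after EoT.
- **That the window is about a day, or shortest in patients who fail fastest.** The rule allows a very short window, but no passage gives time to next therapy or links it to rapid progression or toxicity. Any percentage loss for the whole study would rest on assumed inputs.
- **That the protocol's own figures show the window to be too short.** The 17-hour half-life in section 1.5.1 comes from a single 30 mg dose. Five half-lives are 5 × 17 = 85 hours, about 3.5 days, so it would bear only on switches within the first few days. The 2 weeks in Table 1 is a limit on recovery from an event that has already begun, not a period in which new events are expected.

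The conclusion rests on the text of 3.2.2 and the EoT rule alone. Only how often it matters depends on the unknown switch times.

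**What to change.** Keep the early EoT visit and the routine AE cut-off.

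1. **Section 3.2.2.** State that any SAE, including death, that the investigator judges related to HBI-8000 is reported after EoT whenever the investigator learns of it, regardless of new therapy. Align 2.6.4 and 2.6.6 by cross-reference.
2. **Flagging.** Mark each such event as beginning before or after the subsequent-therapy start date already recorded under 2.6.5.
3. **Section 5.10.1.** Tabulate deaths within 30 days of the last dose from the dosing and survival data, and say how this relates to on-study deaths. State the end of the treatment-emergent period, so that readers can see that it varies.

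The cost is amendment wording and one derived table. A few events confounded by the next therapy will be captured, and the flag makes them visible. The reporting change cannot recover events in patients already past EoT, and patients who have withdrawn from the study entirely remain outside it. Extending collection to all SAEs through day 30 regardless of causality would be a larger trade-off against confounded attribution and is not needed to close this gap.

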3.2.3 Preexisting Conditions

A preexisting condition will not be reported as an AE unless the condition worsens by at least one CTCAE grade during the study. However, the pre-existing condition must be recorded in the screening eCRF as a pre-existing condition, and all concomitant medication administered for the condition must be recorded as concomitant medication in the eCRF following guidelines for other concomitant medication.

3.2.4 Documentation and Reporting of Adverse Events by Investigator

Any signs and symptoms that occur after obtaining the informed consent will be described as AEs and graded according to the CTCAE in the AE section of the eCRF.

Abnormal laboratory values will be recorded on the laboratory section of the eCRF and not in the AE section. Abnormal laboratory results leading to a clinical diagnosis will be reported with a clinical term by the investigator and recorded in the AE section of the eCRF in addition to the laboratory section. Abnormal laboratory results that meet the definition of an SAE should also be reported on an SAE form. Relationship (reasonable causal relationship) to drug treatment and countermeasures taken will be noted on the eCRF. Investigators must record in the eCRF their opinion concerning the relationship of the AE to study therapy.

Disease progression should not be recorded as an AE. Diagnostic and therapeutic non-invasive and invasive procedures, such as surgery, will not be reported as an AE, but the procedure and/or therapeutic treatment should be recorded on the appropriate eCRF. The medical condition for which the procedure was performed must be reported.

3.2.5 Assessment of Causal Relationship to Study Drug

The relationship of an AE to the study medication is graded as follows:

Definite:

- Distinct temporal relationship with the study drug
- Stops/improves when the study drug has been stopped
- Can reasonably be explained by known characteristics of the drug

Probable:

- Reasonable temporal sequence from the study drug administration
- Stops/improves when the study drug has been stopped
- Event cannot easily be explained by patient's clinical state or other factors

Possible:

- Reasonable temporal relationship with the study drug
- Event could have been produced by the patient's clinical state or other factors

Unlikely:

- Poor temporal relationship to the study drug
- Patient's clinical state is likely to have an association with the effect

Unrelated:

- Definitely not associated with the study drug administered

“Definite”, “Probable” and “Possible” events are regarded as AEs that cannot be denied a causal relationship to the study drug, that will be handled as “related to the study drug” for reporting purposes, and “Unlikely” and “Unrelated” events are regarded as AEs that can be denied a causal relationship to the study drug, that will be handled as “not related to study drug” for reporting purposes.

3.2.6 Intensity of Adverse Events

The intensity of adverse changes in clinical signs or symptoms will be graded according to the CTCAE. For all other AEs not described in the CTCAE criteria, the intensity will be assessed by the investigator using the following categories:

Grade 1:

- Mild; asymptomatic or mild symptoms; clinical or diagnostic observations only; intervention not indicated

Grade 2

- Moderate; minimal, local, or noninvasive intervention indicated; limiting age-appropriate instrumental activities of daily living (ADL). Instrumental ADL refer to preparing meals, shopping for groceries or clothes, using the telephone, managing money, etc.

Grade 3

- Severe or medically significant but not immediately life-threatening; hospitalization or prolongation of hospitalization indicated; disabling; limiting self-care ADL. Self-care ADL refer to bathing, dressing and undressing, feeding self, using the toilet, taking medications, and not being bedridden

Grade 4

- Life-threatening consequences; urgent intervention indicated

Grade 5

- Death at least possibly related to the AE

3.2.7 Events Requiring Immediate Reporting

3.2.7.1 *Serious Adverse Events*

Adverse events classified as “serious” must be reported in timely fashion to comply with regulatory requirements. All suspected unexpected serious adverse reactions associated with the use of HBI-8000 will be reported to the regulatory authorities in accordance with the Guideline for Industry International Council for Harmonisation (ICH) E2A, Clinical Safety Data Management: Definitions and Standards for Expedited Reporting.

All SAEs must be recorded in the eCRF within 24 hours of investigator awareness of the event. In particular, if the SAE is fatal or life-threatening, notification to the sponsor must be made within 24 hours, irrespective of the extent of available AE information. In case the eCRF cannot be used by investigator to generate the SAE/Pregnancy form, a paper SAE/Pregnancy form will be used and will be faxed to [REDACTED]. Once the eCRF limitation is resolved, the investigator should enter all the information from the paper report into the eCRF as soon as possible.

[REDACTED]

This timeframe also applies to additional new information (follow-up) on previously forwarded SAE reports. For all SAEs, the investigator is obligated to pursue and provide information to the sponsor in accordance with the timeframes for reporting specified above. In addition, an investigator may be requested by the sponsor to obtain specific additional follow-up information in an expedited fashion. In general, this will include a description of the AE in sufficient detail to allow for a complete medical assessment of the case and independent determination of possible causality. Information on other possible causes of the event, such as concomitant medications and illnesses must be provided. In the case of death, a summary of available autopsy findings must be submitted as soon as possible to the sponsor. All SAEs occurring in this study requiring expedited regulatory reporting will be evaluated, summarized, and reported to investigators. These SAEs must also be submitted in writing by investigators to the institutional review board (IRB).

3.2.7.2 *Pregnancy*

If a patient becomes pregnant during treatment or within 1 month following the last dose of the study drug, administration (if still ongoing) must be discontinued and the sponsor is notified within 24 hours of investigator awareness of the pregnancy. For the purposes of this study, pregnancy of any patient will be considered an AE but not, in itself, an SAE, and should be reported to the sponsor on a pregnancy form rather than an SAE form. However, if pregnancy leads to an SAE for example, a spontaneous abortion or miscarriage resulting in medical hospitalization, an SAE form should be completed. Every attempt must be made to follow the pregnancy to resolution, which includes birth or termination of the pregnancy. If the information is available, the resolution must be reported to the sponsor on a pregnancy form. If possible, births should be followed by the investigator for 8 weeks for observation of any congenital abnormalities, and any such abnormalities should be reported within 24 hours of investigator awareness of the observation to the sponsor.

Pregnancy of a male patient's partner will not be considered an AE, and the male patient should not be withdrawn from the study. If a male patient's partner becomes pregnant during the specified time period (from first dose until 3 months after the last dose), the investigator will inform the sponsor within 24 hours of investigator awareness of the pregnancy, as well as the IRB, as appropriate, and will provide appropriate medical follow-up, if agreed to by the partner.

3.2.7.3 *Overdose*

Overdose is defined as administration to the patient of a dose of test article that exceeds by more than 40 mg/dose or 80 mg/week.

Any overdose of HBI-8000 should be reported via an SAE form within 24 hours of investigator awareness of the overdose to the sponsor, regardless of association with an AE. In the case that the overdose did not result in an AE, the investigator should report this as "overdose, no AE" on the SAE form and specify the intended amount, as well as the actual amount, of drug administered.

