2.7 Study Drug Administration

During this trial, patients will receive 40 mg HBI-8000 administered approximately 30 minutes after any regular meal as four 10 mg tablets BIW continuously. The dosing interval would be 3 to 4 days for a total of 80 mg over 7 days. At each visit when study medication is dispensed, the study site staff will contact the Interactive Web Response System (IWRS) before dispensing.

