2.12 Treatment Compliance

The prescribed dosage, intervals between doses, and mode of administration, e.g., after meals, intact tablet (not crushed) may not be changed without direction by the investigators. They must be recorded in the eCRFs.

The patient will be provided with a drug log to record date and time of administration, time of meal prior to administration, AEs, and missed doses. To verify compliance, the patient will be instructed to bring the drug log and study drug bottles (including any empties) to appointments scheduled for Day1 of each cycle starting with Cycle 2 for reconciliation.

At each visit when study medication is dispensed previously dispensed study drug count will be confirmed by the investigator, or authorized designee, and compliance assessed prior to dispensing new study medication.

Patients exhibiting poor compliance as assessed by tablet counts and not following dosing schedules should be counseled on the importance of good compliance to the study dosing regimen. Noncompliance to drug amount is defined as taking <75% or >125% of study medication during a cycle. Noncompliance to dosing interval is defined as more than 2 occurrences of <3 days between doses during a cycle, for example, 1 or 2 days between doses #3 and #4 instead of 3 or 4 days according to a BIW schedule. If in the opinion of investigator a patient is unable to follow instruction, study treatment should be discontinued.

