3.2.8 Follow-Up of Adverse Events

Patients should be asked to specifically describe any signs, symptoms, or AEs (regardless of relationship to therapy) they may notice prior to the start of the study or thereafter. At a minimum, patients should be asked to report AEs at each visit to the study site. Conditions that the patient experienced prior to informed consent should be recorded in the medical history section of the eCRF.

Follow up of an “overdose” should include continued monitoring of all protocol-specific laboratory results, including chemistry and hematology, using the protocol-specified time points for laboratory tests, with the exception that an additional full series of chemistry, hematology, and coagulation tests, a full physical examination, vital signs, and ECG should be conducted within 24 hours of investigator awareness of that the patient received an “overdose”. Following this additional ad hoc re-evaluation, the investigator should use his or her medical judgment in deciding whether additional supplemental medical treatment is needed to treat adverse medical consequences of the overdose. Also after the ad hoc re-evaluation, the investigator should use his or her medical judgment in deciding whether additional supplemental monitoring is needed to track resolution of any AEs or other abnormal findings to the point of resolution to a CTCAE Grade 1 AE.

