3.4 Blood Volume

The total blood volume for each patient to be collected at screening is approximately 20 mL. Blood volume collected for safety tests on Days 1, 8, 15, and 22 of Cycle 1 will be approximately 30 mL. Assuming each patients would receive up to 6 Cycles of treatment, subsequent cycles will have blood collections for safety tests on Days 1 and 15 of Cycle 2 then Day 1 of Cycles 3 to 6. The total blood collection volume for Cycles 2 to 6 will be approximately 58.5 mL. The total blood collection volume for EoT will be approximately 6 mL for safety tests. For patients participating in PK study, blood volume for PK would be 30 mL for Cycle 1, 15 mL for Cycle 2 and 2 mL pre-dose on Day 1 of Cycles 3 to 6. For patients receiving treatment Cycle 7 and beyond, there will be no PK blood sample except for 10.5 mL blood for safety tests. The assumptions are listed in Table 2 and Table 3.

Table 2: Screening Cycle 1

	Number of Samples	Sample Volume (mL)	Total Volume (mL)
Hematology	5	2	10
Serum chemistry	5	4	20
Coagulation	3	4.5	13.5
Hepatitis B virus tests	1	2	2
Hepatitis C virus tests	1	4	4
Total (excluding PK)			49.5
Pharmacokinetics	10	3 ^a	30
Total (PK participating patients)			79.5

PK: pharmacokinetic

^a The sample volume of 3 mL includes 1 mL of blood needed for flushing the catheter tubing prior to a sample collection.

Table 3: Cycles 2 to 6

	Number of Samples	Sample Volume (mL)	Total Volume (mL)
Hematology	6	2	12
Serum chemistry	6	4	24
Coagulation	5	4.5	22.5
Total (excluding PK)			58.5
Pharmacokinetics cycle 2 day 1	5	3 ^a	15
Pharmacokinetics cycles 3-6 day 1	4	2	8
Total (PK participating patients)			81.5

PK: pharmacokinetic

^a The sample volume of 3 mL includes 1 mL of blood needed for flushing the catheter tubing prior to a sample collection.

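### The overdose definition names no reference dose; read literally, it does not count a doubled 40 mg dose as an overdose, although a fixed ceiling was probably meant

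*Combined protocol and SAP*

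**What the plan says.** Section 3.2.7.3 defines overdose as "administration to the patient of a dose of test article that exceeds by more than 40 mg/dose or 80 mg/week". The verb has no object. The same section requires every overdose to be reported on an SAE form within 24 hours of awareness, whether or not an adverse event occurred. Where there was none, the investigator is to "specify the intended amount, as well as the actual amount, of drug administered".

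The other places that mention overdose set duties but give no definition. Section 3.2.1.2 says "this event should be reported on an SAE form and sent to the sponsor in an expedited manner". Section 3.2.8 adds a full set of chemistry, hematology and coagulation tests, and says that "a full physical examination, vital signs, and ECG should be conducted within 24 hours of investigator awareness".

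The planned regimen is in section 2.7: 40 mg "as four 10 mg tablets BIW continuously". The section continues: "The dosing interval would be 3 to 4 days for a total of 80 mg over 7 days". Section 2.6.8 allows reductions to 30 mg and then 20 mg.

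**The concern.** The sentence can be applied in two ways. Under a **ceiling** rule, any dose above 40 mg or any week above 80 mg is an overdose. Under an **excess** rule, the amount taken must be more than 40 mg above the intended dose, or more than 80 mg above the intended week. The two rules disagree on the most foreseeable error with home dosing, a doubled dose.

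This definition is the trigger for two duties that apply even when the patient is well: the 24-hour report and the 24-hour work-up. A site that follows the literal wording need do neither after a doubled 40 mg dose without an adverse event.

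What is lost depends on when the error comes to light. Patients bring the drug log and bottles "to appointments scheduled for Day1 of each cycle starting with Cycle 2 for reconciliation". If the error is found then, most of the work-up is already scheduled for that day, and mainly the report is at risk. If the site learns of it between visits, both are at risk.

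**Working it through.** The plan gives no figure to reproduce, so the check applies each rule to the same events.

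**Inputs.** Limits of 40 mg per dose and 80 mg per week, both strict (3.2.7.3); 40 mg per dose, 10 mg tablets, 80 mg per 7 days (2.7); reduced doses of 30 and 20 mg (2.6.8); 28-day cycle (2.4); drug-amount noncompliance below 75% or above 125% per cycle (2.12).

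**Rules.**
- Ceiling: actual dose > 40 mg, or actual week > 80 mg.
- Excess: actual − intended > 40 mg per dose, or > 80 mg per week.

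**Thresholds at 40 mg twice weekly, in 10 mg steps.**
- Ceiling: from 50 mg (5 tablets) per dose, or 90 mg per week.
- Excess: dose > 40 + 40 = 80 mg, so from 90 mg (9 tablets); week > 80 + 80 = 160 mg, so from 170 mg.

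**Events.**

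| Event | Dose / week (mg) | Ceiling | Excess |
|---|---|---|---|
| One 40 mg dose doubled | 80 / 40 + 80 = 120 | Yes | No: 80 − 40 = 40; 120 − 80 = 40 |
| Both 40 mg doses in a week doubled | 80 / 160 | Yes | No: 40; 160 − 80 = 80 |
| One 90 mg intake, then 40 mg | 90 / 130 | Yes | Yes: 90 − 40 = 50 |
| One 30 mg dose doubled | 60 / 90 | Yes | No: 30; 90 − 60 = 30 |
| One 20 mg dose doubled | 40 / 60 | No | No: 20; 60 − 40 = 20 |

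**Where the rules disagree at 40 mg.** The two limbs are joined by *or*, so an event caught by either limb counts. Single intakes of 50, 60, 70 and 80 mg change class as long as the week's total stays at or below 160 mg. Weekly totals of 90 to 160 mg change class only if no single intake reaches 90 mg; the third row shows a week of 130 mg caught under both rules.

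**Does the compliance rule catch it?** A cycle is 8 doses, 8 × 40 = 320 mg. One doubled dose gives 360/320 = 112.5%. A doubled week gives 400/320 = 125% exactly, which is not above 125%. Neither is flagged.

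**Wait for the next scheduled tests.** Section 3.4 places safety bloods "on Days 1 and 15 of Cycle 2 then Day 1 of Cycles 3 to 6". From Cycle 7 it gives 10.5 mL of blood for safety tests, which equals 2 + 4 + 4.5 mL, one set of hematology, chemistry and coagulation. An error learned of just after a Day 1 visit could therefore wait up to about 28 days (visit window ±7 days).

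**Who is still exposed.** If the planned last-patient-in date was met at the latest on 30 September 2018, that patient would have been 1,023 days in on 19 July 2021, the date of version 6.0: 1,023/28 = 36.5, so Cycle 37, with one scheduled visit per cycle.

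**Check on a ceiling by week.** Alternating 3- and 4-day gaps (days 1, 4, 8, 11) give two doses, 80 mg, in each 7 days. Two consecutive 3-day gaps (days 1, 4, 7) are also permitted and give 3 × 40 = 120 mg within 7 days. A weekly ceiling needs an exemption for this.

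**The case against.** The strongest reply is that the intent is plain. Section 2.7 has the same two numbers in the same two units, and an overdose rule that starts only above twice the dose would be odd. On this view the word *by* is a slip, and the matter is copy-editing. The point about intent stands. It does not settle the matter, because the slip sits in the threshold that sites must apply, and nothing else in the protocol defines the term.

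Four further replies have force.
- The instruction to record intended and actual amounts is needed under either rule, so it does not favour the excess reading; only the words *by more than* do.
- The low end of the disputed band is within earlier experience: section 1.6 describes HBI-8000 as generally well tolerated up to 50 mg twice weekly, about 100 mg a week. Intakes of 60 to 80 mg lie above that.
- One entry in the table of changes for version 5.0 is marked as applying to the English text only. Sites may therefore work from another language version, and whether it has the same slip is unknown.
- The documents do not say how many patients were still on treatment in July 2021.

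**Conclusion.** The point holds as a minor but operative wording defect. For a patient on 40 mg twice weekly, the literal rule leaves out single intakes of 50 to 80 mg and weekly totals of 90 to 160 mg with no intake of 90 mg or more, all of which the probable intended rule includes. When there is no adverse event, the 24-hour report and the section 3.2.8 work-up would not be triggered for them. This assumes that a site applies the English sentence as written; how sites in fact apply it is not known.

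A reader might infer more than the documents support:
- That the sponsor chose a threshold above double dosing. The match with section 2.7 points the other way.
- That every weekly total from 90 to 160 mg is in dispute. A week containing a 90 mg intake is an overdose on both readings.
- That overdoses have gone unreported or patients have been harmed. No such case is shown, AE and SAE collection continues as usual, and investigators may order tests at their discretion.
- That the trial's results are affected. The definition has no part in the response endpoint, the analysis sets or the sample size.

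**What to change.** Delete *by* in section 3.2.7.3 and state: *a single dose of more than 40 mg, or more than 80 mg in total in a dosing week, where dosing weeks are consecutive fixed 7-day periods counted from Cycle 1 Day 1; doses of 40 mg or less taken at the permitted 3- to 4-day interval are not an overdose.*

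The last clause is needed because doses on days 1, 4 and 7 put 120 mg into one fixed week without any departure from the schedule. A doubled 20 mg dose (40 mg) remains outside this wording, as it is under both readings of the current text.

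The change is one sentence, in an amendment or a safety letter, with the same correction in any translated version that needs it. It will produce a few more overdose reports. Accrual was planned to end in 3Q 2018, so the benefit is limited to patients still on treatment. Version 6.0 keeps treatment open until commercial supply is available after approval, with completion planned for 2Q 2022.
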